## 2. INTRODUCTION

#### 2.1. INTRODUCTION OF THE INVESTIGATIONAL DRUG

BLU-554 capsules, also known as BLU111362 or X439161, are a highly potent selective small molecule inhibitor of FGFR4, which are developed by Blueprints for the treatment against HCC and other solid tumors with positive FGF19 expression.

CS1001 injection is a completely humanized IgG4-type recombinant anti-Programmed death ligand 1 (PD-L1) monoclonal antibody developed by CStone Pharmaceutical, which exerts an antitumor effect by recovering T-cell immune killer function after blocking the PD-L1 signaling pathway. It is currently developed for indications of advanced solid tumors such as HCC, lung cancer, gastric cancer, esophageal cancer etc.

#### 2.2. MECHANISM OF ACTION AND BACKGROUND

#### • Background

#### Hepatocellular Carcinoma

Primary liver cancer mainly includes three different pathological types, which include Hepatocellular Carcinoma (HCC), Intrahepatic Cholangiocarcinoma (ICC) and HCC-ICC, with great differences in the terms of pathogenesis, biological behavior, histologicalmorphology, treatment method and prognosis, with hepatocellular carcinoma accounting for > 85-90%[2]

HCC is the sixth most common cancer and the second leading cause of death in subjects with cancer, which accounts for 7% of all cancers worldwide. Each year, 750,000 subjects could be present with HCC, among which almost 700,000 cases of subjects die [1] HCC is the fourth most common malignant tumor in China and the third leading cause of death in subjects with tumor [2]. Each year, 466 thousand cases of subjects could be present with newly diagnosed HCC in China, among which, about 422 thousands cases of subjects could die[3], which significantly threats to the lives and well-beings of the people in China.

#### Treatment of HCC

Treatment of HCC is based on the staging of the disease. The Barcelona Clinic Liver Cancer (BCLC) staging criteria [4], having been validated in a large series of subjects [5], have become the standard by which treatment decisions are made. At this time, only tumor resection and liver transplantation are curative for HCC. It has been estimated that, in the US, 20–30% of subjects who present with HCC may fall into the very early, or early stages of the

BCLC criteria[1], and so would be candidates for surgical treatment. However, only about 5% of subjects present with very early HCC, where resection and transplant have had the best results, and in many others presenting with early stage disease, chronic liver disease and cirrhosis preclude the use of surgery as a treatment modality. Even in subjects who are thought to be good candidates and successfully undergo resection, recurrence rates can be 55% at 2 years, and may reach 60-100% by 5 years[6]. Localized therapies such as trans-arterial chemo-embolization have had some long-term success, but only in very select groups of subjects.

The majority of subjects with HCC ultimately require systemic therapy, but development of systemic treatment for HCC has been severely limited. The current standard of care is sorafenib, a multikinase inhibitor, which received marketing approval in 2007. Sorafenib was evaluated in two Phase 3 trials against a control of best supportive care (BSC), with one trial conducted in

Western subjects with HCC, and the other in subjects from the Asia-Pacific region. In the Western trial, median overall survival (OS) improved from 7.9 months in the BSC arm to 10.7 months in the sorafenib arm (hazard ratio 0.69, p <0.001) reflecting an improvement of 30% [7]. In the Asia-pacific trial, a similar degree of improvement was seen, although with a subject population with more advanced disease, the actual survival times were different (4.2 months in the BSC arm vs. 6.5 months in the sorafenib arm) [8].

Although other multi-kinase inhibitors including linifanib, sunitinib and brivanib have been tested as first-line treatment for HCC, none has shown a statistically significant improvement in OS compared to sorafenib in Phase 3 studies [9][10][11]. Lenvatinib was approved by the FDA as first-line treatment for HCC in August 2018. In a non-inferiority Phase III study of lenvatinib versus sorafenib, the results showed that the median survival was 13.6 months in the lenvatinib arm and 12 months in the sorafenib arm (HR, 0.92; 95% CI, 0.79-1.06), indicating that the lenvatinib was not inferior to sorafenib [12]. However, this was accompanied by significant toxicity and frequent dose interruptions and reductions [13].

In the second-line treatment for HCC in subjects who have received prior sorafenib, the multikinase inhibitor, regorafenib, and the PD-1 inhibitor, nivolumab have shown clear clinical activity and gained approval in the second line setting [14][15]. However, ORR and

OS remain low with these agents and there are no diagnostics to select subjects more likely to benefit. Thus, there remains a substantial medical need for novel agents for the systemic treatment for HCC in both the first and second line settings.

Immune checkpoint is a class of molecules that are immunosuppressed. Their physiological function is to regulate the intensity and breadth of immune response, thereby avoiding damage of normal tissue. While tumor cells tend to utilize such profile of the immune checkpoints to evade attacks of the immune cells. Currently, the immune checkpoints that have been clinically validated include CTLA-4 and PD1/PD-L1, and the immune checkpoint inhibitors targeting the PD1/PD-L1 have better clinical application prospect due to their better safety and broader indications. The combination with many types of drugs is possible due to the good safety and potential improvement of immune micro-environment properties of PD1/PD-L1 inhibitors. PD1/PD-L1 inhibitors in combination with many types of drugs has also been explored in multiple clinical studies, including anti-PD1/PD-L1 inhibitors in combination with CTLA-4 inhibitors such as nivolumab in combination with ipilimumab, durvalumab in combination with tremepilimumab; PD1/PD-L1 inhibitors in combination with molecular targeted agents such as lenvatinib in combination with pembrolizumab, PDR-001 in combination with sorafenib. It was reported that lenvatinib in combination with pembrolizumab had a response rate of 52. 2% in subjects with advanced endometrial cancer and 63% in subjects with renal cell carcinoma, indicating that the combination regimen has the more prospective clinical treatment prospects [16]

[figure not shown]
• BLU-554

BLU-554 was designed as a highly potent, selective small molecule inhibitor of FGFR4 and has a unique selectivity profile for the FGFR family.

In normal physiology, FGF19 controls bile acid homeostasis and promotes hepatocyte survival and proliferation via binding to FGFR4 and co-receptor, Klotho-beta (KB), which initiates activation of the extracellular signal-regulated kinase (ERK) signaling pathway (**Figure 1**) [17]. Extracellular signal-regulated kinase activation attenuates bile acid

production by repressing expression of cholesterol- $7\alpha$ -hydroxylase (CYP7A1), an enzyme which catalyzes the first and rate-limiting step of bile acid production from cholesterol.

Extracellular signal-regulated kinase additionally promotes hepatocyte proliferation via EGR1 and hepatocyte survival via anti-apoptotic mechanisms.

# Figure 1:FGF19-FGFR4 Pathway in Normal Physiology and HCC

The FGF19 pathway normally functions as an endocrine system in which post-prandial bile acids trigger FGF19 production in the ileum for delivery to the liver via the portal circulation. Liver expresses high levels of FGFR4 and KLB, which bind the released FGF19 and initiate signaling. Hepatocellular carcinomas likely to remain FGF19 responsive, suggesting that targeting the FGF19 pathway may have therapeutic benefit in HCC.

• CS1001

PD-L1, primarily expressed on the surface of tumor cells and antigen presenting cells, is the main ligand of T-cell inhibitory receptor PD-1 [18]. Binding of PD-L1 on tumor cells to PD-1 on the surface of T cell may cause signaling cascade reaction, inhibiting the proliferation of T cells and secretion of activated cytokines, reducing the activity of T cells, and reducing the tumor-cell killing ability of T cells; PD-L1 inhibitors impair the activity of T cells and tumor-cell killing ability by blocking the interaction between PD-1 and PD-L1 [19].

CS1001 is a completely humanized IgG4-type recombinant anti-Programmed death ligand 1 (PD-L1) monoclonal antibody, which exerts an anti-tumor effect by recovering T-cell immune killer function after blocking the PD-L1 signaling pathway.

### 2.3. PRECLINICAL STUDY

### 2.3.1. PHARMACOLOGY

[figure not shown]
### 2.3.1.1. BLU-554

### Inhibition of FGFR4 In Vitro

BLU-554 was designed as a highly potent, selective small molecule inhibitor of FGFR4 and has a unique selectivity profile for the FGFR family. BLU-554 forms a covalent interaction with cysteine 552 of FGFR4. This cysteine is located near the adenosine triphosphate (ATP)

binding site in FGFR4 and is unique among FGFR family members as well as rare among other kinases. It demonstrated biochemical in vitro activity on the FGFR4 kinase domain at a half-maximal inhibitory concentration (IC50) of 5 nM and is at least 100-fold less active against the other FGFR paralogs. No kinases outside of the FGFR family are significantly bound by BLU-554. **Figure 2** below shows the high selectivity of BLU-554 across the human kinome.

# Figure 2: The Activity of BLU-554 against the Human Kinome

[figure not shown]

Each branch of the dendrogram above represents an individual human kinase. BLU-554 was screened at 3  $\mu$ M against each kinase. Kinases inhibited at 3  $\mu$ M are indicated by red circles on the kinome tree. The degree of inhibition corresponds to the size of the circle. No kinases outside of the FGFR family are significantly bound by BLU-554. Kinome illustration reproduced courtesy of Cell Signaling Technology, Inc (www.cellsignal.com).

In vitro, in human breast cancer cell line MDA-MB-453, BLU-554 exhibited dose-dependent inhibition of FGFR4 activity as well as modulation of key effector pathways known to be involved in tumorigenesis.

### Inhibition of FGFR4 In Vivo

[figure not shown]
In vivo, anti-tumor efficacy with BLU-554 was demonstrated in a Hep3B human HCC xenograft model (genomic amplification and overexpression of FGF19) and in a LIX-066 subject-derived tumor xenograft model (overexpression of FGF19 without amplification). In the Hep3B model **Figure 3**), tumor regression was observed following administration of BLU-554 on both once daily (qd) and twice daily (bid) dosing schedules with no corresponding weight loss. In the LIX-066 primary human tumor model (**Figure 4**), tumor stasis was observed with a significant reduction in tumor growth upon administration of BLU-554; efficacy and tolerability were improved compared to sorafenib. Together, these data provide a rationale for selecting subjects with FGF19 overexpression and/or gene amplification for treatment with BLU-554.

### Figure 3:BLU-554 Efficacy in a Xenograft Tumor Model with Amplified FGF19

Mice bearing Hep3B xenograft tumors were dosed orally on a once daily (qd) or twice daily (bid) schedule with 30, 100, or 200 mg/kg BLU-554. The Hep3B xenograft models HCC tumors that are IHC+, FISH+. BLU-554 100 mg/kg bid and 200 mg/kg qd resulted in equivalent tumor growth inhibition. Data points represent group mean and error bars represent standard error of the mean (SEM).

# Figure 4:Efficacy Measurements for BLU-554 in a Subject-derived Xenograft Tumor Model with FGF19 Up-regulation in the Absence of Genomic Amplification

Mice bearing LIX-066 xenograft tumors were dosed orally with 30, 100, or 200 mg/kg BLU- 554 bid. The LIX-066 xenograft models HCC tumors that are IHC+, FISH-. A significant decrease in tumor growth was observed. Data points represent group mean, and error bars represent standard error of the mean (SEM).

Safety pharmacology studies revealed that BLU-554 inhibits human ether-a-go-go-related gene (hERG) channel activity in vitro with an average IC50 of 6.26  $\mu$ M by single cellular electrophysiological recordings. The pharmacologic specificity of BLU-554 was assessed against a panel of 55 pharmacological targets including receptors, transporters, and enzymes. Compound binding was calculated as percentage inhibition of the binding of a radioactively labeled ligand specific for each target. Assays for the following targets showed >50% inhibition by BLU-554 at 10  $\mu$ M screening concentration: A3 adenosine receptor,  $\alpha$ 2 adrenergic receptor, chloride ion channel,  $\kappa$ -opioid receptor,

CSTONE Confidential Page 40 of 139 melatonin receptor MT1, sodium ion channel site 2, and the nociceptin receptor. The relevance of this binding was not apparent in the dog and mouse 28-day Good Laboratory Practice (GLP) toxicology studies and so the clinical significance of these interactions is unknown.

# 2.3.1.2. CS1001

### In Vitro Pharmacology

*In vitro* pharmacology studies were conducted, including: the binding capacity with cell surface human PD-L1, the binding capacity with recombinant PD-L1 protein in human, cynomolgus monkey or mouse, the binding kinetics to recombinant PD-L1 protein, the binding capacity with human PD-L2 protein, the member of PD-L1 family, competitive blocking of ligation of PD-L1 with PD-1/CD80, activation on human CD4+ T cells, ADCC and CDC.

In the binding assay of PD-L1 on the cell surface, CS1001 antibody effectively bound to PD-L1-transfected CHO cells with an EC50 value being 1.10 nM.

Cross-species reactivity test showed that CS1001 specifically binds to human and cynomolgus monkey PD-L1 protein with the comparable binding capacity, but cannot bind to mouse PD-L1 protein.

The calculated result of affinity with WBP315.hPro1.ECD.mFc showed that CS1001 has strong affinity with PD-L1 protein and its affinity constant is 1.38 nM.

Cross-reactivity assay with proteins of PD-L1 family showed that CS1001 specifically binds to human PD-L1 protein but not to human PD-L2, indicating that this PD-L1 antibody would not potentially cause side effects due to non-specific binding.

From the results of competitive inhibition of PD-L1/PD-1 ligation, it is clear that CS1001 can effectively block the ligation of PD-L1 with PD-1 protein with IC50 value being 1.93 nM. It is also showed that CS1001 can effectively block the ligation of PD-L1 with CD80 similarly as the reference antibody WBP315BMK1 (BMS).

Together, above results showed that CS1001 can inhibit the PD-1/PD-L1 interaction via specific binding to PD-L1. Its effect on T cell immune function was further studied in *in vitro* functional experiments.

The effect of CS1001 on T lymphocyte activation was tested using mixed lymphocyte reaction (MLR). The results showed that CS1001 can significantly enhance the secretion of IL-2 and IFN- $\gamma$  by CD4+ T lymphocytes, and promote the proliferation of CD4+ T lymphocytes.

[figure not shown]
On the other hand, the ADCC and CDC effect of CS1001 were tested. The results indicated that CS1001 had no ADCC and CDC on PD-L1-positive lymphocytes, thereby without potential damage to surrounding immune cells *in vivo*.

### In Vivo Pharmacology

[figure not shown]
Because CS1001 does not recognize mouse PD-L1, the activity of CS1001 was evaluated in a syngeneic mouse tumor model humanized with human PD-L1 in the tumor graft (MC38- B7H1) and human PD-1 in animal host (i.e. B-hPD-1 C57BL/6 humanized mouse). The drug was

administered through intraperitoneal injection, once every 2 days for 6 consecutive doses. The results (**Figure 5**) showed that the tumor volume in the solvent control group increased rapidly during the test period (the mean tumor volume was 2359 mm^3 at the end of the study), while the tumor volumes were substantially lower in the CS1001 low (3mg/kg), medium (10 mg/kg), and high (30 mg/kg) dose groups than the control group (the mean tumor volumes were 949 mm^3, 1416 mm^3, and 1115 mm^3, respectively), and all 3 doses showed effective anti-tumor activity (Tumor Growth Inhibition [TGIs] were 62.8%, 42.0%, and 55.4%, respectively; p=0.019, 0.149, and 0.039, respectively). On the other hand, mice in different groups showed no significant difference in body weight changes during administration (**Figure 6**), and were in good state of activity and food consumption, indicating that the mice were well tolerated with CS1001. The consistent results were achieved in a repeated study using the same animal model.

### Figure 5: Tumor Growth in Each Group during the Test

### Figure 6: Body Weight Changes of Mice in Each Group during the Administration

### 2.3.2. PHARMACOKINETICS

### 2.3.2.1. BLU-554

### Single-Dose Pharmacokinetics

Upon single dose administration in nonclinical species, plasma clearance upon IV administration was moderate in mouse and rat, at ~ 20% liver blood flow. Plasma clearance in nonrodent species, dog, and monkey, was low at  $\leq 20\%$  liver blood flow. The volume of distribution at steady state was low-to-moderate in all species, either approximating or slightly higher than published values for the volume of total body water. The oral bioavailability of BLU-554 dosed as a solution was moderate in mouse, rat, and dog, ranging from 62% to 82%, and was low in monkey (29%).

### Repeat-dose Pharmacokinetics

In repeat-dose toxicology studies in mice, plasma exposure to BLU-554 increased less than proportionally to dose upon repeat-dosing for 7 or 28 days. Systemic exposure to BLU-554 was similar in both sexes of mice (Report WIL-124511).

In repeat-dose toxicology studies in dogs, BLU-554 exposure in terms of  $C_{max}$  increased in a dose proportional manner, but AUC0-24 increased greater than proportionally to dose upon repeat-dosing for 28 days. Exposure was similar in both sexes of dogs (Report WIL-124512).

### 2.3.2.2. CS1001

Single-Dose Pharmacokinetic Study

Serum PK characteristics and ADA on CS1001 were assessed when 18 male and 18 female navïe cynomolgus monkeys were administered intravenously once at 10, 30 and 90 mg/kg.

The results showed that in the dose range of 10 mg/kg to 90 mg/kg, the C0 of CS1001 increased in a dose-dependent manner, and the rate of AUC0-last increased greater than proportional over the above-mentioned dose range.

The female: male ratio of CS1001 systemic exposure (AUC0-last) (**Table 2**) was 0.58, 0.94 and 0.85 in the low, medium and high dose groups respectively, all of which were within 2 folds, suggesting that no significant gender difference on CS1001 systemic exposure in cynomolgus monkeys.

ADA was mainly occurred at 648, 984 and 1320 hours after administration; in the 10 mg/kg treatment group, the number (%) of monkeys with a positive ADA sample was 22.2% for both male and female, and in the 30 mg/kg treatment group, the number (%) of monkeys with a positive ADA sample was 22.2% for the male and 11.1% for the female. No monkeys had positive ADA sample in the 90 mg/kg treatment group. The data showed that compared with the low-dose group, the positive rate of ADA in the high-dose group showed a decreasing trend. No abnormalities were observed in all the experimental animals during the whole experiment.

Please refer to Investigator's brochure (IB) of CS1001.

# 2.3.3. TOXICOLOGY

### 2.3.3.1. BLU-554

The toxicity profile of BLU-554 was evaluated in vitro in a bacterial reverse mutation assay and in vivo in CD-1 mice, Sprague-Dawley rats, and Beagle dogs. CD-1 mice and Beagle dogs were chosen as the nonclinical test species for assessing chemical structure- and pharmacology-mediated toxicity of BLU-554 on the basis of the following criteria: a) these species are pharmacologically responsive to the effects of BLU-554; b) these species have historically been utilized to assess potential human adverse effects, and; c) these species are qualitatively similar in hepatocyte metabolism profiles to humans.

### Repeat-Dose Toxicity

In the 28-day GLP-compliant repeat-dose toxicology study in CD-1 mice, only minimal effects were noted at a limit dose of 2,000 mg/kg/day. Resultant end-of-study sex-averaged maximum plasma concentration ( $C_{max}$ ) and area under the plasma concentration versus time curve from 0 to 24 hours (AUC0-24) in the mouse were higher than the predicted  $C_{max}$  and AUC0-24 at the projected human efficacious dose of 1,000 mg/day; (581 mg/m^2/day).

In the 28-day GLP-compliant repeat-dose toxicology study in Beagle dogs, the lethal dose effects, the highest non-severely toxic dose (HNSTD) effects, and the dose-limiting toxicities (DLT) have been carefully characterized. In the dog, the DLT is attributed to inanition, gastrointestinal malfunction, and metabolic perturbations evidenced by changes in body weights, food consumption, serum, and urine chemistry values, and contributed to by hematologic and tissue effects. The severely toxic dose (STD) in the dog is 50 mg/kg/day (1,000 mg/m^2/day) and the HNSTD is 25 mg/kg/day (500 mg/m^2/day). At the HNSTD, the predominant change in serum biochemistry was hyperphosphatemia. However, this was modest (maximum increase of 30% on Day 15) and readily reversible, with complete recovery by Day 42. Hyperphosphatemia was

CSTONE Confidential Page 44 of 139 associated with minimal to mild tissue mineralization as detailed in the Investigator's Brochure. Effects noted in dogs are considered to be related to the pharmacologic activity of FGFR4 signaling by BLU-554 or the sequelae of these effects, except for the myxomatous change noted in the heart. All adverse effects are monitorable. All adverse effects were resolving or resolved after the 14-day recovery period, except effects in the stomach, heart, and aorta. No functional effects on the cardiovascular system were noted based on electrocardiogram (ECG) analyses and in-life examinations.

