### Toxicokinetics

The allometrically scaled HNSTD in the dog is  $500 \text{ mg/m}^2$  (25 mg/kg/day). The highest nontoxic dose in the mouse is 2,000 mg/kg/day or 6,000 mg/m^2. Based on allometrically scaled dosages as well as on systemic exposures (AUC0-24), the dog is the most sensitive species. The

mouse tolerates these exposures without toxic consequences. The mean exposure in the dog at the HNSTD approximates the steady state  $AUC_{0-24}$  and  $C_{max}$  values at the human MTD/RP2D of 600 mg/day (370 mg/m^2/day), while the STD exposure  $AUC_{0-24}$  and  $C_{max}$  values exceed the maximum tolerated human exposure.

See Investigator's brochure (IB) of BLU-554 for more details.

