### MTD = Maximum Tolerated Dose

During the study period, an SMC consisting of the principle investigator, the CRO's representatives (CRA and other relevant person) and the sponsor's representative will be established to review the safety data, PK data, efficacy data from the study and determine the escalation dose level and dosage regimen in dose escalation study so as to determine the MTD, recommend dose levels in the extension study, and determine the RP2D. The SMC will also decide whether or not to include unscheduled dose levels for the study.

Once the RP2D is determined in phase Ib, the protocol will be amended to explore the safety and efficacy of the combination regimen in HCC subjects. Currently, Phase Ib study has been completed for subject recruitment on May 20, 2020, and SMC has confirmed the RP2D as

BLU-554 600 mg QD combined with CS1001 1200 mg IV Q3W on June 18, 2020 by reviewing the relevant safety, PK and efficacy data of subjects enrolled in Phase Ib study.

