## 7.1.5. Laboratory Tests

The blood and urine samples used for clinical laboratory assessment will be collected as specified by the protocol. The specific collection time points are described in the SOA. Details of sample preparation and analysis will be provided by local laboratories. The reference ranges for all safety parameters will be provided by local laboratories.

This study will detect the following parameters;

Blood test	Platelet Count	Platelet Count		RBC Indices:		WBC count with Differential:		
	RBC Count		MCV		Neutrophils			
	Hemoglobin		МСН		Lymphocytes			
	Hematocrit				Monocytes			
			E		Eosinopl	Eosinophils		
					Basophil	S		
Serum Chemistry	BUN/Urea 	Pota	assium	AST ALT Alkaline phosphatase		Total and direct bilirubin		
	Creatinine	Sod	lium			Total protein		
	Glucose	Cal	cium			Albumin		
						Total cholesterol		
						Triglyceride		
CK-MB	CK-MB							
HBV, HCV  , HIV	HCV antibody, HBsAg and HIV antibody							
AFP	AFP							
Coagulation	PT, INR and aPTT							
Routine Urine Test	pH, Specific gravity, Glucose, ketones, WBC, protein							
Thyroid Function	FT3, FT4 and TSH							
immunogenicity	ADA level							
FGF19, PD-L1 expression	FGF19 IHC、PD-L1							
Pregnancy test 	β-hCG							

1. The detection of this test item for the same patient in the same study site should be consistent throughout the study.

2. Subjects with HBsAg positive will further assess HBV DNA test, subject with HCV antibodypositive will further assess HCV RNA test.

3. A serum pregnancy test should be performed for female subjects at Screening; thereafter, a serum or urine pregnancy test should be performed on every odd cycle (e.g. C3, C5).

As for unexpected clinical laboratory detection values or values with unknown cause, if the investigator judges them as clinically significant, they should be repeatedly detected within 24h and continuously followed up until the detection results return to their normal value range and/or a rational explanation is found for such abnormality. The clinical laboratory will clearly mark the detection values beyond the normal value range, and the principal investigator needs to judge whether these abnormal values are clinically significant one by one, record those clinically significant ones as AEs and elaborate their relationship with treatment.

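### Serum phosphate is missing from the scheduled chemistry panel, although a modest, reversible phosphate rise was the main chemistry change in dogs at about the exposure of the RP2D

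*Protocol*

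**What the plan says.** **Dog finding.** Protocol Section 2.3.3.1, Repeat-Dose Toxicity, states: "At the HNSTD, the predominant change in serum biochemistry was hyperphosphatemia". It qualifies this at once: "this was modest (maximum increase of 30% on Day 15) and readily reversible, with complete recovery by Day 42". It also says the finding was "associated with minimal to mild tissue mineralization as detailed in the Investigator's Brochure". Apart from a myxomatous change in the heart, it attributes the dog effects to FGFR4 pharmacology or its consequences. It then states: "All adverse effects are monitorable".

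**Exposure.** The Toxicokinetics paragraph of the same section says: "The mean exposure in the dog at the HNSTD approximates the steady state" AUC and Cmax at a human dose of 600 mg/day. It calls the dog the most sensitive species.

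**Dose in this trial.** Section 4.3.1 records that the safety monitoring committee confirmed the RP2D as "BLU-554 600 mg QD combined with CS1001 1200 mg IV Q3W on June 18, 2020".

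**Laboratory panel.** Section 7.1.5 introduces its table with "This study will detect the following parameters". The serum chemistry row lists urea, creatinine, glucose, potassium, sodium, calcium, AST, ALT, alkaline phosphatase, total and direct bilirubin, total protein, albumin, total cholesterol and triglyceride.

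**Use of the results.** Laboratory tests belong to the safety endpoint in both phases (Section 3). Protocol 10.3 and SAP 3.5.5 summarise the laboratory values that are collected.

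**The concern.** The protocol identifies one serum chemistry effect as the leading one in its most sensitive species, treats the dog effects as mostly on-target, and places the exposure at about that of the dose being expanded. The panel then measures calcium but not phosphate. A modest phosphate rise would not be expected to announce itself clinically, so without a scheduled test little would prompt anyone to look.

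What is at stake is the completeness of the safety description, not the efficacy result. SAP 3.5.5 can show change from baseline, grade shifts and abnormal listings only for analytes that were measured. For phosphate it would have nothing systematic to show, so the final report could neither describe the effect in the combination nor say that it was absent.

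**Working it through.** No sample-size or power formula applies. The check sets the relevant sections side by side and uses simple arithmetic.

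1. **Dog study timeline.** 28 days of dosing + 14 days of recovery = Day 42. This agrees with the day on which recovery was complete.

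2. **Exposure relation.** The Toxicokinetics paragraph says that dog exposure at the HNSTD and human exposure at 600 mg/day are approximately equal; it gives no numerical ratio. By body surface area the doses are 500 mg/m² (dog, 25 mg/kg/day) and 370 mg/m² (human, 600 mg/day): 500 / 370 = 1.35. The near-equality therefore rests on the stated AUC and Cmax comparison, not on mg/m². It refers to 600 mg/day of BLU-554 without CS1001.

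3. **Panel count.** Counting total and direct bilirubin separately, the serum chemistry row of 7.1.5 has 15 analytes. None is phosphate or phosphorus. Alkaline phosphatase is an enzyme test and does not measure phosphate.

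4. **Other places it might be scheduled.** The following do not name serum phosphate:
   - the schedules of activities (protocol Tables 2 to 5, repeated in SAP Appendix 2)
   - the visit lists in 7.5
   - the treatment-adjustment text in 6.4
   - SAP 3.5.5

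5. **Treatment ceiling (the plan's own figure).** 35 cycles × 21 days = 735 days; 735 / 30.4375 = 24.15 months. The stated 24 months is reproduced.

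6. **Scheduled chemistry draws for a subject who completes 35 cycles.**
   - Phase II on treatment: 2 in Cycle 1 (Days 1 and 15) + 34 (Day 1 of Cycles 2 to 35) = 36. With screening, EOT and safety visit 1: 36 + 3 = 39.
   - Phase Ib on treatment: 3 in Cycle 1 (Days 1, 8, 15) + 2 in Cycle 2 (Days 1, 15) + 33 (Cycles 3 to 35) = 38.
   - No chemistry is scheduled at C1D2 or at safety visits 2 and 3.

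   The samples needed are therefore already being taken.

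7. **What the human data can exclude.** Section 2.4.1.1 lists drug-related events at a 20% threshold among 115 subjects: 0.20 × 115 = 23. A related event in fewer subjects than that need not appear. The section does not say whether phosphate was measured.

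**The case against.** The strongest reply is that the omission may be deliberate and informed. The dog rise was modest and reversible, and the tissue change minimal to mild. After the dog study, 115 subjects received BLU-554, 81 of them at 600 mg in Part 2, and the protocol's safety summary does not mention phosphate. Section 2.5 names gastrointestinal events and liver enzyme or bilirubin elevation as the human concerns. The Investigator's Brochure, which the protocol cites for detail, is not available here. All this stands as a reason to rank the point low. It does not show that phosphate is unnecessary: the summary covers common events and the main SAEs, and neither document gives a reason for leaving phosphate out.

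A reader might also infer more than the documents support:

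- **That no case could be detected.** Footnote a of Tables 2 and 3 allows extra safety tests when clinically indicated, and Section 8.2 sets out when an abnormal result is reportable. What is missing is scheduled measurement.
- **That the monitorability statement contradicts the panel.** It says the effects can be monitored, not that this trial schedules a test for each. The two sections fit poorly together, but they do not contradict each other.
- **That the stomach, heart and aorta effects, which had not resolved after recovery, were the mineralization.** Section 2.3.3.1 does not link them.
- **That subjects will typically go two years without a test.** 735 days is a ceiling. In the monotherapy study, 105 of 115 subjects (91%) had stopped treatment by the cut-off, 78 of them for progression.

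**Conclusion.** The point holds as a cheap improvement to safety monitoring. At about the exposure of the confirmed RP2D, the leading serum chemistry change in dogs has no scheduled measurement in this trial: 0 of 15 chemistry analytes, and 0 of up to 36 on-treatment chemistry draws per Phase II subject. The safety summaries could not describe phosphate systematically.

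The clinical size of the effect cannot be estimated. The documents give no human incidence, so any expected number of cases would be invented. The MTD, the ORR analysis and the go/no-go criteria do not depend on phosphate.

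The conclusion assumes that the published table in 7.1.5 is complete, that no laboratory manual or eCRF specification outside these documents already includes phosphate, and that the monotherapy exposure comparison is a fair guide to the combination.

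**What to change.** Add serum inorganic phosphate to the serum chemistry row of protocol 7.1.5. Run it on the samples already drawn wherever Tables 2 and 3 schedule chemistry (so not at C1D2 or safety visits 2 and 3). Report it with the other analytes under SAP 3.5.5. If the sponsor has data showing that it is not needed, a sentence saying so in 7.1.5 would reconcile that section with 2.3.3.1.

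The cost is one routine analyte, one eCRF field and one more row in the laboratory tables, with no new visit or blood draw. The main limitation is timing. Phase Ib recruitment closed on May 20, 2020, so no Phase Ib subject would have a baseline value, and neither would any Phase II subject already dosed; for them, change from baseline could not be shown. No dose or clinical management rule is proposed.
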